The univariate and multivariate Cox regression analysis is used to identify important risk factors for the failure of dental implants and to develop the model. Then, the performance of the models, in aspects of calibration and discrimination, is assessed. Calibration is defined as the agreement between predicted outcomes and observed outcomes. For assessment of calibration, the included implants are separately grouped into deciles based on their predicted risk of failure. The calibration of the model is assessed by plotting the predicted risk of failure against 1 minus the individual Kaplan-Meier estimate for each decile in the follow-up. Discrimination is defined as the ability of the model to differentiate between those with and without outcome events. The discrimination of the model in the follow-up is assessed with the concordance index (C-index). Then, the model is converted to a score chart and line chart in order to facilitate the calculation of the failure rate of implants. The score of each included predictor is produced by the regression coefficients being divided by the smallest regression coefficient among the predictors and subsequently rounded. Finally, the clinical values of the model are assessed, using prevalence, sensitivity, specificity, positive predictive value (PPV), and negative predictive value (NPV) of the model at the optimal cutoff score.

All the statistical procedures are performed with SPSS software 25.0 (IBM, New York, the USA) and R software 3.2.3 (R Development Core Team, Vienna, Austria).

What is already known:

Recently, there are many studies focusing on the evaluation of survival rate of implants based on longitudinal cohorts. However, they mainly reported the values of the failure rate of implants in the follow-up (like 5-year survival rate) or compared the failure rate of different types of implants. These types of studies are beneficial for the groups of patients but not for the individual patients. Also, there are several studies focusing on the prognostic factors that may be associated with the survival rate of dental implants. But these studies belonged to prediction factor studies instead of prediction modeling studies. The findings in these studies are difficult to directly apply to clinical practice.

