However, there is a very limited number of studies focusing on the prediction of survival rate (or failure rate) of implants in the follow-ups. For example, Chuang et al. (1) used a clustered marginal approach to predict the survival rate in 2002 and found that among those who had a delayed procedure, did not smoke, and underwent a two-stage implant procedure, the predicted 1- and 5-year survival rates were 97.2% and 93.4%, respectively. For those who had an immediate implant placed, smoked, and underwent a one-stage procedure, the predicted survival rates were 58.5% and 27.6%, respectively. In 2006, Chuang and Cai (2) used Cox proportional hazards frailty model to predict the future implant survival based on some predictors including smoking status, the timing of placement of the implant and implant staging.

In this study, they predicted that for a non-smoking individual with 2 implants placed, an immediate implant and in one stage, the probability that 1 implant would survival 12 months was 85.8% and the joint probability of surviving for 12 months was 75.1%. If 1 implant was placed earlier and had survived for 12 months, then the second implant had an 87.5% chance of surviving 12 months. However, in these two studies, the authors only included a small number of predictors and did not develop a score chart for the individual patients. Also, the performance of the models was not assessed.

What is the project will add:

The project can provide clinicians with the predicted probability of the failure rate of dental implants of each individual patient preoperatively. The model may be helpful for clinicians to make decisions about the postoperative care for the patients. Also, the model can help shape the patients' expectations about the survival of dental implants.

What is new:

In the project, we will use some more predictors to predict the survival rate of dental implants to make the prediction model more accurate. Also, we will develop a score chart for clinicians. In this score chart, clinicians can easily calculate the sum score of each patient and find out the corresponding predicted probability of the failure rate of dental implants of each individual patient. The score chart is very easy-to-use in the clinical practice. Besides, in this project, the methodology (the prediction model developed with Cox regression analysis) is novel in dentistry.

References:

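### The plan cannot show whether the added predictors improve accuracy, because only the new model is assessed, apparently in its own development data

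*Combined protocol and SAP*

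**What the plan says.** Under *What is already known*, the protocol describes two earlier prediction studies. The later one predicted implant survival from "some predictors including smoking status, the timing of placement of the implant and implant staging". Of both, the protocol says that "in these two studies, the authors only included a small number of predictors and did not develop a score chart for the individual patients". It adds: "Also, the performance of the models was not assessed". Under *What is new* it then states: "we will use some more predictors to predict the survival rate of dental implants to make the prediction model more accurate".

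The *Statistical analysis* section describes how the model is built: "The univariate and multivariate Cox regression analysis is used to identify important risk factors for the failure of dental implants and to develop the model". For calibration, "the included implants are separately grouped into deciles based on their predicted risk of failure", and predicted risk is plotted against the Kaplan-Meier failure estimate in each decile. For discrimination: "The discrimination of the model in the follow-up is assessed with the concordance index (C-index". The model then becomes a score chart, and sensitivity, specificity and predictive values are given at an optimal cutoff.

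No section plans a reference model, a nested test, a difference in C-index, an application of an earlier model to this cohort, a bootstrap, cross-validation, a split sample or external data. The cohort size, the number of failures, the number of candidate predictors and the selection threshold are not stated.

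**The concern.** Saying that more predictors give better accuracy is a comparison, and a comparison needs a second model. The plan has one. The earlier studies cannot supply the benchmark, because by the protocol's own account their performance was not assessed. They are also described as predicting implant survival, whereas the *Outcomes* section here counts peri-implantitis and mobility as failure too and starts the clock at placement of the suprastructure.

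The performance measures that are planned cannot stand in for the comparison. Calibration uses the included implants, and no other data are named for the C-index. A C-index computed in the data that produced the coefficients is optimistic, and the optimism grows with the number of predictors fitted or screened.

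At stake is the length of the chart. Clinicians are meant to score individual patients preoperatively. Whether a longer list of items predicts better than a short one decides which chart they should be given, and the plan would not tell them.

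**Working it through.** The documents give no figure to reproduce: no sample size, event count or target C-index. Every numerical input below is therefore an assumption.

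**Measures.** C = (concordant pairs + 0.5 × tied pairs) / usable pairs. Likelihood-ratio gain = 2 × (log-likelihood of the larger model − log-likelihood of the reference model).

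**Assumed inputs for the main simulation.** Three real binary predictors with log hazard ratios 0.5, 0.4 and 0.4; 5 or 15 added predictors that are pure noise; 500, 1,000 or 2,000 implants with about 10% failing; 100 runs per setting. C is computed in the development data and in 4,000 new implants. The screened variant keeps only noise predictors with univariate p<0.10, a threshold that the plan does not give.

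| Added noise predictors | Failures (about) | Apparent C, reference → larger | Change | New-data C, reference → larger | Change |
|---|---|---|---|---|---|
| 15, all kept | 50 | 0.613 → 0.693 | +0.080 | 0.581 → 0.548 | −0.033 |
| 15, all kept | 100 | 0.606 → 0.653 | +0.047 | 0.593 → 0.567 | −0.026 |
| 15, all kept | 200 | 0.605 → 0.633 | +0.028 | 0.594 → 0.578 | −0.016 |
| 5, all kept | 50 | 0.614 → 0.649 | +0.035 | 0.586 → 0.566 | −0.020 |
| 5, all kept | 100 | 0.608 → 0.628 | +0.020 | 0.593 → 0.582 | −0.011 |
| 5, all kept | 200 | 0.604 → 0.615 | +0.011 | 0.598 → 0.592 | −0.006 |
| 15, screened | 50 | 0.617 → 0.656 | +0.039 | 0.587 → 0.569 | −0.018 |
| 15, screened | 100 | 0.604 → 0.626 | +0.022 | 0.591 → 0.577 | −0.014 |
| 15, screened | 200 | 0.600 → 0.614 | +0.014 | 0.596 → 0.591 | −0.005 |

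Apparent C rose in 100% of runs with 15 unscreened noise predictors, in 96% to 99% with 5, and in 80% to 85% with screening. In new data the larger model was worse in 90% to 95%, 76% to 88% and 62% to 76% of runs respectively.

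**Separate check** (1,000 implants, 15 noise predictors, about 132 failures). Apparent C went from 0.626 to 0.659 and new-data C from 0.619 to 0.595. With screening at p<0.10, the larger model's figures were 0.639 and 0.609.

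**Stricter selection** (15 binary noise predictors, about 122 failures, univariate p<0.10 then multivariable p<0.05, both assumed). About one noise item was kept. Apparent C went from 0.632 to 0.643 (+0.011) and new-data C from 0.625 to 0.617 (−0.008).

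**Strong added predictors.** With three of the added predictors at hazard ratio 2.0, new-data C rose from 0.616 to 0.682 (+0.066) in one check, and from 0.63 to 0.69 in another with about 278 failures. With hazard ratio 1.5 per standard deviation and about 290 failures, it rose from 0.62 to 0.71.

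**Likelihood-ratio benchmark.** Fifteen noise predictors are expected to give a gain of about 15, their degrees of freedom; simulated averages were 15 to 16. By AIC, 15 extra parameters must gain more than 2 × 15 = 30.

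The simulations treat implants as independent and ignore clustering within patients.

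**The case against.** The sentence is rationale. The *Aim* is to identify risk factors and develop a prediction model, and no hypothesis, outcome or analysis claims superiority. The comparison with earlier models is inferred from the preceding paragraph, and the protocol offers other advances, such as the score chart. This stands: the gap does not undermine developing the model.

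A reader might infer that the plan would display a false improvement. It would not. It fits no smaller model, so it shows no gain of any kind. The rise in apparent C bears on how to interpret the one C-index that will be reported.

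A reader might also infer that the added predictors are useless or harmful. The documents do not support that. Under *Predictors*, candidates are screened by literature, guideline and expert opinion, so an all-noise list is an extreme case. Any selection step reduces the damage, as the screened rows show, and strong predictors clearly help.

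Finally, a three-factor model refitted here is not one of the earlier models. The protocol says that their predictors included those three, so the list may be incomplete, and the outcome and time origin differ. This also stands, and it limits what the comparison may be called. None of it supplies the missing evidence that the added predictors improve accuracy.

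**Conclusion.** The concern holds as a limited one: the accuracy statement has no planned analysis behind it. Nothing in the plan separates a real gain from optimism.

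The size depends on quantities that the documents do not give. When the added predictors are noise, the assumed settings give an apparent rise in C of 0.011 to 0.080 and a new-data fall of 0.005 to 0.033, with the smaller values under more failures, fewer predictors or selection. When a few added predictors are strong, new-data C rises by about 0.06 to 0.09 (0.69 − 0.63 and 0.71 − 0.62). The documents give no ground for preferring either case.

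It would go too far to say that the project will end by wrongly claiming to beat the published models, or that a longer chart will predict worse. The text neither commits to the first nor gives the effect sizes needed for the second.

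**What to change.** 1. Pre-specify a reference Cox model in the same implants and with the same failure outcome, containing smoking status, timing of placement and staging, as far as they are recorded. Keep these factors in the larger model so that the two are nested.
2. Report the likelihood-ratio gain with its degrees of freedom, calculated for all added candidates, since counting only those that survive selection understates the degrees of freedom.
3. Report the difference in C-index and in calibration (for example the calibration slope) with confidence intervals from a bootstrap that resamples patients, not implants, and repeats the predictor selection in each resample. A reference model without this correction would not be enough, because the apparent difference favours the larger model.
4. Call the result the incremental value of the added predictors in this cohort, not superiority over the earlier published models.
5. Remove or soften the accuracy wording under *What is new* if the corrected difference does not support it.

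The cost is one more Cox fit and a bootstrap on data that are being extracted anyway, plus a few sentences. Eligibility and outcome stay as they are. The result may be less favourable to the larger model.
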